This is a randomized, double-blind, placebo-controlled, parallel-group, Phase 3 study to evaluate the efficacy and safety of PF-04965842 in adolescent participants 12 to <18 years of age with moderate-to-severe AD. Participants will be screened within 28 days prior to the first dose of study intervention to confirm study eligibility. Approximately 225 participants will be randomized in a 1:1:1 ratio to receive once daily PF-04965842 at 200 mg, 100 mg, or placebo for 12 weeks.

This study includes an immunogenicity sub-study integrated into the last 4 weeks of the main study treatment period. At Week 8, up to approximately 90 participants (up to approximately 30 in each treatment arm) who have completed 8 weeks of treatment with study intervention will receive a tetanus, diphtheria and acellular pertussis combination vaccine (Tdap), and collection of blood samples for the evaluation of immunogenicity at Weeks 8 and 12. Participants of this sub-study will complete all other protocol-specified procedures in the main study.

At the end of the 12-week study treatment, qualified participants completing the study will have the option to enter the long-term extension (LTE) study B7451015. Participants discontinuing early from the study will undergo a 4 week follow-up period.

Disclosure Statement:

This is a Parallel Treatment study with 3 Arms that is Investigator, Sponsor and Participant blinded.

Number of Participants:

Approximately 225 participants will be randomized in the study; of those up to approximately 90 participants will participate in the immunogenicity sub-study between Week 8 and Week 12.

Intervention Groups and Duration:

Eligible participants will be randomized into 3 intervention groups in the main study:

Group 1 (N=75): 200 mg PF-04965842 once daily (QD) for 12 weeks (Sub-study: N=up to 30, Tdap vaccination at Week 8)

090177e19618b8f7\Approved\Approved On: 25-Jan-2021 08:51 (GMT)

[figure not shown]
Group 2 (N=75): 100 mg PF-04965842 QD for 12 weeks (Sub-study: N=up to 30, Tdap vaccination at Week 8)

Group 3 (N=75): placebo QD for 12 weeks (Sub-study: N=up to 30, Tdap vaccination at Week 8)

The total duration of participation in the study, including the integrated sub-study, is up to 20 weeks, including up to 4 weeks for screening, 12 weeks study intervention and a follow-up period of 4 weeks after study intervention (for those participants that do not enter the LTE study).

Data Monitoring Committee: Yes

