1.3. Schedule of Activities (SoA)

Visit Identifier	Screening		Intervention Period								Follow-up		Notes
	Day -28	Visit 1	Day 1	Day 8	Day 15	Day 29	Day 43	Day 57	Day 85	Day 113	Week 16 (EOS)		
			Week 0 Baseline (by Phone)	Week 1 (by Phone)	Week 2	Week 4	Week 6 (by Phone)	Week 8	Week 12 (EOT/ET)				
	Visit 1	Visit 2	Visit 3	Visit 4	Visit 5	Visit 6	Visit 7	Visit 8	Visit 9			Visit 9 is 4 weeks after last dose in case of early study termination	
Visit Window (days)	None	None	±1	±1	±2	±3	±3	±3	±3				
Enrollment Procedures													
Informed consent/assent	X												
Register subject using IRT	X												
Inclusion and exclusion criteria	X		X										
Demographics, Medical History, Tobacco and Alcohol History, AD Disease History and prior AD treatments	X												
Review Prior/Concomitant Medications & Treatments	X	X	X	X	X	X	X	X	X	X	X		
Dispense eDiary and instruct participants on use	X												

Visit Identifier	Screening	Intervention Period										Follow-up	Notes	
		Day -28	Day 1	Day 8	Day 15	Day 29	Day 43	Day 57	Day 85	Day 113	Week 16 (EOS)			
Instruct participants on washout of pre-baseline medications (if applicable)	X													See inclusion criteria #3 (Section 5.1) and exclusion criteria #16 (Section 5.2)
Train participants on use of background topical therapy for AD and daily recording in eDiary	X	X	X	X	X	X	X	X	X	X	X			See Section 6.5.1
Provide Patient Emergency Contact Card	X													
Medical Procedures														
Complete physical examination	X	X								X				See Section 8.2.1
Targeted Physical Exam				X	X					X		X		
Vital Signs (pulse rate, blood pressure, temperature)	X	X		X	X					X		X		See Section 8.2.2 Temperature collection applies to Germany and UK only. Temperature data will be recorded in source documents only.
Weight	X	X										X		See Section 8.2.1
Height	X											X		See Section 8.2.1

Visit Identifier	Screening	Intervention Period								Follow-up	Notes
		Day -28	Day 1	Day 8	Day 15	Day 29	Day 43	Day 57	Day 85		
	X	Week 0 Baseline (by Phone)	Week 1 (by Phone)	Week 2	Week 4	Week 6 (by Phone)	Week 8	Week 12 (EOT/ET)	Week 16 (EOS)		Visit 9 is 4 weeks after last dose in case of early study termination
Chest Imaging / X-Ray	X										Recommended but not mandatory For Germany only: If chest imaging is considered medically necessary, MRI may be performed.
ECG (12-lead)	X	X		X	X		X	X	X		Central reading
Laboratory Procedures											

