2.2.3. Summary of PF-04965842 Clinical Pharmacokinetics

PF-04965842 was rapidly absorbed following single dose oral solution/suspension administration over the dose range 3 mg to 200 mg with time to maximum absorption (T_{max}) ranging between 0.55 to 0.77 hours (B7451001). Median T_{max} at doses of 400 mg and 800 mg was 1.5 and 3.9 hours, respectively, which indicated slower absorption compared to lower doses. PF-04965842 showed a monophasic decline at dose < 100 mg with biphasic profiles at doses ≥ 100 mg. Observed maximum plasma PF-04965842 concentrations (C_{max}) following the single dose administration generally increased in proportion to the dose from 3 mg to 800 mg. In contrast, both area under the plasma concentration time curve from time zero extrapolated to infinity (AUC_{inf}) and area under the plasma concentration time profile from time zero to the last quantifiable concentration (AUC_{last}) were dose proportional in the range of 3 mg to 200 mg, while a greater than proportional increase was observed at doses of 400 and 800 mg. The arithmetic mean terminal phase half-life ($t_{1/2}$) was 1.9 to 4.9 hours.

Following QD administration over the dose range 30 mg to 400 mg and 100 mg and 200 mg twice a day (BID) for 10 days, median T_{max} ranged between 0.50 to 0.77 hours

(B7451001). After attainment of C_{\max} , the disposition of PF-04965842 was consistent with that observed following single-dose administration, showing a biphasic decline following all but the lowest dose and an arithmetic mean terminal phase $t_{1/2}$ between 2.8 to 5.0 hours. The observed accumulation ratio (R_{ac}) for area under the curve over dosing interval tau (AUC_{τ}) and C_{\max} following QD dosing was minimal (between 1.1 and 1.5), consistent with the prediction from $t_{1/2}$. Urinary recovery of PF-04965842 was low, with <5% of the dose recovered unchanged in urine across all doses and regimens in all cohorts.

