
- b. Female participants:

A female participant is eligible to participate if she is not pregnant or breastfeeding, and at least one of the following conditions applies:

- Is not a woman of childbearing potential (WOCBP) (see definition in Appendix 4)

OR

- Is a WOCBP (all female participants, regardless of whether or not they have experienced/reported menarche, are considered WOCBP unless they are permanently sterile or confirmed infertile). A WOCBP who is sexually active must use a contraceptive method that is highly effective, with a failure rate of $<1\%$, as described in Appendix 4 during the intervention period and for at least 28 days after the last dose of study intervention. The investigator should evaluate the effectiveness of the contraceptive method in relationship to the first dose of study intervention.
- A WOCBP must have a negative highly sensitive (Appendix 2) serum pregnancy test at the screening visit. A urine pregnancy test with a sensitivity of at least 25 mIU/mL, will be performed before the first dose of study intervention and at every site visit including the EOT and follow-up visits to confirm the subject has not become pregnant. If a urine test cannot be confirmed as negative (eg, an ambiguous result), a serum pregnancy test is required. In such cases, the participant must be excluded from participation if the serum pregnancy result is positive.
- The investigator is responsible for review of medical history, menstrual history, and recent sexual activity to decrease the risk for inclusion of a woman with an early undetected pregnancy.

Informed Consent

8. Capable of giving signed informed consent/assent as described in Appendix 1 which includes compliance with the requirements and restrictions listed in the informed consent form (ICF) and in this protocol.
9. Willing and able to comply with scheduled visits, treatment plan, laboratory tests and other study procedures.

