5.3.3.2. Guidance Regarding Household Contact Vaccine-Related Exposure

Current routine household contact with children and others who have been vaccinated with live vaccine components may pose a risk during treatment and for 6 weeks following completion of the study. Some of these vaccines include varicella (“chickenpox”) vaccine, oral polio vaccine, and the inhaled flu vaccine. Following vaccination with live component vaccines, the virus may be shed in bodily fluids, including stool, and there is a potential risk that the virus may be transmitted. General guidelines for immunosuppressed participants suggest that exposure (through routine contact) should be avoided following vaccination (of others) with these vaccines for the stated time period:

- a. Varicella or attenuated typhoid fever vaccination for 4 weeks following vaccination.
- b. Oral polio vaccination for 6 weeks following vaccination.
- c. Attenuated rotavirus vaccine for 10 days following vaccination.
- d. FluMist[®] (inhaled flu vaccine) for 1 week following vaccination.
- e. Measles, Mumps and Rubella vaccine for 4 weeks following vaccination.
- f. Yellow fever vaccine for 4 weeks following vaccination.

The list of live vaccines in this section is not exhaustive. For questions on household contacts who have received other live vaccines, such as dengue vaccine, please contact Pfizer clinician.

Participants should avoid exposure to vaccinated or infected persons and contact the investigator promptly should they develop signs or symptoms of infections.

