8. STUDY ASSESSMENTS AND PROCEDURES

- Study procedures and their timing are summarized in the Schedule of Activities. Protocol waivers or exemptions are not allowed.
- Immediate safety concerns should be discussed with the sponsor immediately upon occurrence or awareness to determine if the participant should continue or discontinue study intervention.
- Adherence to the study design requirements, including those specified in the Schedule of Activities, is essential and required for study conduct.
- All screening evaluations must be completed and reviewed to confirm that potential participants meet all eligibility criteria. The investigator will maintain a screening log to record details of all participants screened and to confirm eligibility or record reasons for screening failure, as applicable. Participants will be screened (Visit 1) within 28 days prior to administration of the study intervention to confirm that they meet the participant selection criteria for the study. The investigator (or an appropriate delegate at the investigator site) will obtain informed consent from each participant, or parent(s)/legal guardian (and assent from the participant, as appropriate), in accordance with the procedures described in Section 10.1.3.
- Screening laboratory tests with abnormal results may be repeated once to confirm abnormal results; the last value will be used to determine eligibility. If results return to normal within the 4-week screening period, the participant may enter the study.
- Due to possible need for PPD testing and chest radiograph, screening procedures may be performed over more than 1 visit in the 28 days prior to the Day 1 visit.
- Visit windows are based on Day 1 visit. To assure consistency and reduce variability, all study visits should occur in the morning whenever possible. On days of study visits, participants will receive their dose at the clinic during the visit.
- When possible, participants should fast for at least 8 hours prior to all visits that include lipid profile panel testing (Day 1, Week 4, Week 12, and EOS). During the fasting period, participants should refrain from all food and liquids (water and permitted non-study medications are allowed).
- ECGs will be interpreted by a central reader for all visits.
- Urine pregnancy test must be performed prior to dosing with the study intervention for WOCBP through the EOT visit.

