8.3.1. Time Period and Frequency for Collecting AE and SAE Information

The time period for actively eliciting and collecting AEs and SAEs ("active collection period") for each participant begins from the time the participant provides informed consent, which is obtained before the participant's participation in the study (ie, before undergoing

any study-related procedure and/or receiving study intervention), through and including a minimum of 28 calendar days; except as indicated below after the last administration of the study intervention.

For participants who are screen failures, the active collection period ends when screen failure status is determined.

AEs and SAEs that begin before the start of the study intervention but after obtaining informed consent are recorded on the Medical History/Current Medical Conditions section of the case record form (CRF), not the AE section. AEs and SAEs that begin from the first administration of the study intervention are recorded on the AE CRF. SAEs are also reported on the CT SAE Report Form from the time of obtaining informed consent is signed.

Follow up by the investigator continues throughout and after the active collection period and until the event or its sequelae resolve or stabilize at a level acceptable to the investigator, and Pfizer concurs with that assessment.

Investigators are not obligated to actively seek AE or SAE after conclusion of the study participation. However, if the investigator learns of any SAE, including a death, at any time after a participant has been discharged from the study, and he/she considers the event to be reasonably related to the study intervention or study participation, the investigator must promptly notify the sponsor.

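### For completers not entering the LTE, the last scheduled contact can fall 22 to 34 days after the last dose, so up to 6 days of the 28-day safety collection period may have no planned contact

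*Protocol*

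**What the plan says.** The protocol synopsis (Section 1.1) describes "a follow-up period of 4 weeks after study intervention (for those participants that do not enter the LTE study". The Schedule of Activities (Section 1.3) puts Visit 8 (Week 12, end of treatment) at Day 85 and Visit 9 (Week 16, end of study) at Day 113, each ±3 days. Section 8 gives the anchor: "Visit windows are based on Day 1 visit". The only text that ties the final visit to dosing is a note in the schedule: "Visit 9 is 4 weeks after last dose in case of early study termination". It does not extend to completers.

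A completer's last dose is taken at Visit 8. Section 8 has doses given in clinic on visit days, and Section 8.5 takes a PK sample two hours after dosing at Week 12.

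The safety periods run from the last dose:
- Section 8.3.1: "The time period for actively eliciting and collecting AEs and SAEs" runs "through and including a minimum of 28 calendar days; except as indicated below after the last administration of the study intervention".
- Section 8.3.5.1: pregnancies are collected until 28 days after the last dose.
- Section 5.1 and Appendix 4: contraception applies "during the intervention period and for at least 28 days after the last dose of study intervention".
- SAP Section 3.5.1: an event is treatment-emergent if it starts before the last dose plus a 28-day lag.

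The schedule lists no contact after Visit 9.

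**The concern.** Visit 9 carries the last scheduled AE enquiry and contraception check (Section 1.3) and the last urine pregnancy test (Section 8.2.10). If it falls before post-dose day 28, the remaining days of the collection period have no planned contact. A gap between two earlier visits is covered when the next visit asks what has happened since. No later visit in this study does that for the days after Visit 9.

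Two provisions make this more than a formality. Section 8.3.1 says investigators need not actively seek events once study participation has ended, and Section 4.4 treats a participant as complete once the follow-up assessments are done. A site that holds a compliant but early end-of-study visit could reasonably stop asking. At stake is complete capture of AEs, SAEs and pregnancies over a period that the protocol itself sets, in adolescents taking an immunomodulator.

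**Working it through.** **Inputs.** Visit 8 target Day 85 ±3, Visit 9 target Day 113 ±3 (Section 1.3). Windows counted from Day 1 (Section 8). Last dose on the Visit 8 date (Sections 8 and 8.5). Collection period 28 days (Section 8.3.1). Treatment-emergent lag 28 days (SAP Section 3.5.1). SAP Section 6.2.3.4 also takes Day 88 as the latest Week 12 day, which agrees with 85 + 3.

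**The plan's own figure.** 113 − 85 = 28 days, which reproduces the stated 4 weeks when both visits are on target.

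**Range with both windows in use.** Let d be the study day of the last dose (82 to 88) and v the day of Visit 9 (110 to 116).
- Shortest interval: 110 − 88 = 22 days.
- Longest interval: 116 − 82 = 34 days.

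**Largest shortfall for a given last dose.**
- AE/SAE and pregnancy collection runs through d + 28, so the largest shortfall is (d + 28) − 110 = d − 82.
- The treatment-emergent window takes events *before* last dose plus 28 days. Read by date, it ends on d + 27, so the largest shortfall is d − 83, or 0 if that is negative. If clock times are used, part of one more day is added.
- Visit 9 days at or after post-dose day 28: 116 − (d + 28) + 1 = 89 − d.

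| Last dose (d) | Post-dose day 28 | Max. AE/pregnancy shortfall (days) | Max. TEAE shortfall (days) | Visit 9 days that reach day 28 (of 7) |
|---|---|---|---|---|
| 82 | Day 110 | 0 | 0 | 7 |
| 83 | Day 111 | 1 | 0 | 6 |
| 84 | Day 112 | 2 | 1 | 5 |
| 85 | Day 113 | 3 | 2 | 4 |
| 86 | Day 114 | 4 | 3 | 3 |
| 87 | Day 115 | 5 | 4 | 2 |
| 88 | Day 116 | 6 | 5 | 1 |

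An early final visit does not need a late Visit 8. With the last dose exactly on schedule (Day 85), a compliant Visit 9 on Day 110, 111 or 112 falls before post-dose day 28.

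**Date pairs.** Of the 7 × 7 = 49 compliant pairs, 1 + 2 + 3 + 4 + 5 + 6 = 21 give an interval under 28 days, and one gives 22 days. Six of the 21 have an interval of exactly 27 days and leave no treatment-emergent day uncovered. These are counts of possible pairs, not a forecast.

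**Early terminators.** Their Visit 9 is anchored to the last dose, but ±3 days gives 25 to 31 days, so it can still be up to 3 days short.

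**The case against.** The strongest reply is that the provisions can all be met together. Section 8.3.1 already requires active elicitation to at least 28 days, and the last column of the table never reaches zero, so a site can always book a compliant Visit 9 on or after post-dose day 28. On this view only a reminder is missing.

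Other safeguards also survive an early visit:
- Known events are followed proactively (Section 8.3.3).
- Clinically significant laboratory abnormalities within 28 days of the last dose are repeated (Section 8.2.8).
- SAEs that come to the investigator's attention after the active period are still reported (Section 8.3.1.1).
- Participants are told to call about pregnancy or stopped contraception (Appendix 4) and to "contact the investigator promptly should they develop signs or symptoms of infections" (Section 5.3.3.2).
- The terminal half-life on repeated dosing is short, "between 2.8 to 5.0 hours" (Section 2.2.3).

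Most of this stands, and it is why the point is minor. It does not remove the mismatch. That day 28 can be reached does not mean it must be: for a last dose on Day 88 exactly one of the seven permitted days qualifies, and the schedule does not direct the site to it. For new non-serious events after an early visit, the listed safeguards depend mainly on the participant calling in.

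A reader might go further and infer that events after an early Visit 9 go uncollected by design, or that the protocol contradicts itself. The documents do not support that, because the duty to collect through post-dose day 28 continues after the visit.

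**Conclusion.** The point holds as a minor scheduling mismatch. For completers not entering the LTE, the last scheduled contact can fall 22 to 34 days after the last dose. When it falls before post-dose day 28, up to 6 days of AE/SAE and pregnancy collection have no planned contact. The 6-day figure needs the latest Visit 8 together with the earliest Visit 9, and it should not be carried over to treatment-emergent counting, where the maximum is 5 calendar days.

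This rests on two readings: that a completer's last dose is on the Visit 8 date, and that Day 1 anchors Visit 9 for completers. If the synopsis were taken to anchor Visit 9 to the last dose, the ±3 window would still leave up to 3 days.

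Two stronger inferences are not supported. The 21 of 49 date pairs do not mean that about 43% of completers are affected: the documents give neither the number of completers outside the LTE nor where visits fall within their windows. Nor is a biased comparison of safety between arms shown, since the same schedule applies to all three. Efficacy, power and alpha are untouched.

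**What to change.** For completers not entering the LTE, adopt one of two changes in Protocol Sections 1.3 and 8.

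1. Keep the present window and, when Visit 9 was held before post-dose day 28, require a brief AE and pregnancy telephone check on or after that day. This is the lighter option. It costs one short call for those seen early.
2. Time Visit 9 at actual last dose plus 28 days, -0/+3. Completers would be seen 28 to 31 days after the last dose, between Day 110 (82 + 28) and Day 119 (88 + 31). Re-anchoring with ±3 would not be enough, as the early-terminator case shows. If this option is chosen, the same one-sided window can also apply to early terminators.

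The second option narrows the window from 7 days to 4, which may produce some more out-of-window visits. It also moves the latest completer visit from Day 116 to Day 119. The synopsis gives a total of up to 20 weeks (140 days). Four weeks of screening plus the present windows can already exceed that (28 + 116 = 144 days), and this option would make it 28 + 119 = 147.

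Neither option needs a SAP change: the Week 16 reporting window in SAP Appendix 2 opens at Day 100 and has no upper limit. A protocol change needs IRB/IEC approval (Section 10.1.1), and re-consent if the consent form version changes (Section 10.1.3), so it is best carried in the next planned amendment.

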8.1. Efficacy Assessments

8.1.1. Rater Qualifications

Clinical evaluations of AD will be performed by an experienced and qualified dermatologist (board certified or equivalent). An experienced and qualified non-dermatologist physician or experienced medical professional with experience in the conduct of dermatology clinical trials may be permitted to perform the clinical evaluations of AD when designated by the primary site Investigator. The evaluator must receive and document protocol specific and applicable efficacy assessment scales training prior to performing these evaluations. **To assure consistency and reduce variability, the same evaluator must assess all dermatological clinical evaluations for any individual subject throughout the study whenever possible;** a back-up experienced and qualified, protocol-trained evaluator will only be allowed and documented in case of emergency or special situations when the designated evaluator is unable to perform the evaluation.

